#### **6.5.2 Severe hypersensitivity reactions including anaphylaxis and immune complex disease**

Anaphylaxis is a severe, potentially fatal, systemic allergic reaction that occurs suddenly after contact with an allergy-causing substance, such as investigational product. For the purposes of this study, the definition [REDACTED] is provided as a simple and rapid means to make the diagnosis of anaphylaxis during infusion with investigational product. This definition was a product of a symposium convened by the National Institute of Allergy and Infectious Diseases and Food Allergy and Anaphylaxis Network ([Sampson et al, 2006](#)).

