### **6.6.3 Variables**

The following variables will be collected for each AE;

- AE (verbatim)
- The date and time when the AE started and stopped
- Maximum intensity
- Whether the AE is serious or not
- Investigator causality rating against the investigational product (yes or no)
- Action taken with regard to investigational product
- Outcome of AE

In addition, the following variables will be collected for SAEs:

- Onset Date (Date AE met criteria for serious AE)
- Detection Date (Date Investigator became aware of serious AE)
- AE is serious due to:
  - (a) Death
    - Date of death
    - Autopsy performed
    - Primary/secondary cause of death
  - (b) Life-threatening
  - (c) In-patient hospitalisation or prolongation of existing hospitalisation
    - Date of hospitalisation
    - Date of discharge
  - (d) Congenital abnormality or birth defect
  - (e) Important medical event
  - (f) Suspected transmission via a medicinal product of an infectious agent
- Description of AE
- Investigator causality assessment to concomitant medications
- Investigator causality assessment to study procedures (yes or no)

It is important to distinguish between serious and severe AEs. Severity is a measure of intensity, whereas seriousness is defined by the criteria defined above. An AE of severe intensity need not necessarily be considered serious. For example, nausea that persists for several hours may be considered severe nausea, but not an SAE. On the other hand, a stroke that results in only a limited degree of disability may be considered a mild stroke but would be an SAE. The Investigator should provide an assessment of the severity of each AE/SAE.

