#### **7.2.4 Subject monitoring/procedures during and after the infusion**

Subjects will be monitored during the administration of the investigational product and for at least 2 hours after the first 4 infusions (Visits 1 to 4). For subsequent infusions, if there are no safety concerns, subjects will be monitored during administration of the investigational product and for a minimum of 1 hour after completion of the IV infusion thereafter.

Monitoring will include vital signs (oral temperature, blood pressure, pulse rate, respiratory rate) in a sitting position at the following times:

- Shortly before the IV infusion (within 15 ±5 minutes of the beginning of the investigational product infusion)
- Every 15 ±5 minutes during infusion
- Immediately after completion of administration of investigational product, including post-dose saline flush (within 15 ±5 minutes after completion of investigational product administration)
- Every 30 ±5 minutes after completion of investigational product administration (not including saline flush) for at least 2 hours after the first 4 doses of investigational product are administered (Visits 1 to 4), and for at least 1 hour thereafter

Vital signs may be taken more frequently, based on Investigator judgment.

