### 3.1.1 Adverse events

Adverse events experienced by the subjects will be collected throughout the entire studies and will be coded using the latest version of Medical Dictionary for Regulatory Activities (MedDRA).

Adverse event data will be categorised according to their onset date based on the last dose of administration in either the feeder studies or the LTE, whichever is later, as follows:

In general:

- AEs occurring during treatment:  
An AE during treatment is defined as an AE with a date of onset  $\geq$  day of first dose of investigational product and  $\leq$  date of last dose of investigational product + 28 days.
- AEs occurring during follow-up:  
An AE during follow-up is defined as an AE with a date of onset  $>$  date of last dose of investigational product + 28 days and  $\leq$  date of last dose of investigational product + 84 days.
- AEs occurring during treatment and follow-up:  
An AE during treatment and follow-up is defined as an AE with a date of onset  $\geq$  day of first dose of investigational product and  $\leq$  date of last dose of investigational product + 84 days

The following are exceptions:

- For subjects in the “Randomised Placebo” treatment group with a switch to anifrolumab 300 mg in the LTE study, AEs with a date of onset  $\geq$  day of first dose of investigational product in the LTE study will not be considered in the categories above, except for those with an onset on the day of first dose of investigational product in the LTE that are recorded in the Phase 3 feeder studies.
- For subjects in the “All Anifrolumab” treatment group who were randomised to placebo in the Phase 3 feeder studies, AEs with a date of onset  $<$  day of first dose of investigational product in the LTE study and those with an onset on the day of first dose of investigational product in the LTE that are recorded in the Phase 3 feeder studies will not be considered in the categories above.

In general, an AE during LTE is defined as an AE in the categories above with a date of onset  $\geq$  day of first dose of investigational product in the LTE study. AEs with onset on the day of first dose of investigational product in the LTE, but which were recorded in the Phase 3 feeder studies will not be considered as occurring during the LTE.

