Adverse events with missing intensity will be assumed to be severe. Events with missing relationship to study medication per the investigator will be assumed to be related. If no information about seriousness is available, the AE will be considered serious.

AEs and AEs leading to discontinuation of investigational product during treatment and follow-up will also be presented by time intervals of the first onset of the event. For this analysis, repeated events with the same preferred term will not be considered (i.e., if a subject has more than one event with the same preferred term, only the event with the earliest date of onset will be used). The following time intervals are defined for AEs during treatment and follow-up:

- Year 1:  
AEs with date of onset  $\geq$  date of first administration of investigational product and either  $<$  maximum of date of re-randomisation in LTE study and date of administration of IP in LTE study or from subjects who are not randomised into the LTE study (ie, all AEs documented in the Phase 3 feeder Studies D3461C00004 and D3461C00005 are considered AEs in Year 1). If the AE has an onset on the day of first dose of investigational product in the LTE and is recorded in the Phase 3 feeder studies, it will be considered during year 1.
- Year 2:  
AEs with date of onset  $\geq$  date of first administration of investigational product in LTE study and  $<$  date of first administration of investigational product in LTE study plus 364 days
- Year 3:  
AEs with date of onset  $\geq$  date of first administration of investigational product in LTE study plus 364 days and  $<$  date of first administration of investigational product in LTE study plus 728 days
- Year 4:  
AEs with date of onset  $\geq$  date of first administration of investigational product in LTE study plus 728 days and  $<$  date of first administration of investigational product in LTE study plus 1092 days
- After year 4:  
AEs with date of onset  $\geq$  date of first administration of investigational product in LTE study plus 1092 days

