For time to event analyses and calculation of alternative event rates only, the following rules will be applied for imputing (partially) missing onset dates prior to analysis: If an AE has a (partially) missing onset date, it will be imputed with the earliest possible date on or after the day of first administration of investigational product given the available start and stop date information. If the available start or stop date information indicate that the AE started prior to first administration of investigational product, no imputation of the start date will be done.

For the by timepoint analysis of anaphylaxis, hypersensitivity, and infusion related reactions, an AE at a visit is defined as an AE with a date of onset  $\geq$  day of administration of investigational product at the respective visit and  $\leq$  date of administration of investigational product at the following visit (or  $\leq$  date of last dose of investigational product + 84 days for the last visit with investigational product). Analogous to assignment of AEs to time intervals, AEs with (partially) missing date will be assigned to the earliest possible visit giving the available start and stop date information, in the study (feeder phase 3 or LTE) they were recorded in.

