### 3.3.4 Exposure of investigational product

An infusion of IP is defined as follows:

- Start time and end time of study drug infusion are not missing and start time and end time are not equal, and
- Volume of infusion bag prior to infusion start is greater than volume of infusion bag at the end of infusion or investigator confirmed that study drug was administered according to protocol.

The duration of exposure to the investigational product per subject is defined as the number of days between the start and the end dates of investigational product plus the dosing frequency time:

For the subjects randomised to Placebo in the feeder study who switch to Anifrolumab, the following definition applies, to account for exposure time of the feeder study (placebo) up until the day before their first dose of Anifrolumab in the LTE study:

Duration of exposure (days) = ([first dose date in LTE-1]) – first dosing date in feeder study + 1,

For the All Anifrolumab group the following definition applies, to account only for their exposure time of Anifrolumab:

Duration of exposure (days) = (Last Anifrolumab dosing date + 28 days) – first Anifrolumab dosing date + 1,

For all other subjects, duration of exposure is defined as:

Duration of exposure (days) = (Last dosing date + 28 days) – first dosing date + 1.

Duration of LTE exposure is consequently defined as

Duration of LTE exposure (days) = (Last dosing date of LTE study + 28 days) – first dosing date of LTE study + 1.

The total subject years of exposure is the sum of duration of exposure (days) of all subjects in the respective treatment group divided by 365.25 (days/year).

The total number of infusions and infusions during LTE will be counted per subject.

The time to discontinuation of investigational product is the same as the duration of exposure.

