Cardiovascular outcome events as determined by the CV-EAC will be presented separately, summarising the number of AEs submitted for adjudication and the outcomes of the adjudication including MACE classification. Site reported cardiovascular AEs, cardiovascular SAEs, and their corresponding adjudicated outcomes will be listed.

The time to first onset of an AE in an AESI category will be presented separately for each AESI category as a Kaplan-Meier plot annotated with the number of subjects at risk every 6 months.

Furthermore, the alternative event rates per 100 subject years for the first onset of herpes zoster will be summarized for events overall and by time intervals). The following subcategories will also be considered in this summary: SAE (including events with outcome of death), AE leading to discontinuation, and AE by maximum intensity (mild, moderate, and severe). This summary will also be presented for the additional supportive treatment groups placebo feeder + anifrolumab 300 mg LTE, and anifrolumab 150 mg feeder + anifrolumab 300 mg LTE.

Furthermore, AESIs (by event type and preferred term), SAEs (during treatment and during follow-up separately, by system organ class and preferred term) during LTE will be summarised by LTE treatment group. Summaries of deaths, AESIs by time interval and SAEs by time interval will also be presented for the additional supportive treatment groups placebo feeder + anifrolumab 300 mg LTE, and anifrolumab 150 mg feeder + anifrolumab 300 mg LTE.

The event rate per 100 subject years and number and percentage of subjects with at least one anaphylaxis, hypersensitivity, and infusion-related reaction (investigator), respectively, will be summarised overall as well as for the following respective subcategories: SAE (including events with outcome of death), AE leading to discontinuation, and AE by maximum intensity (mild, moderate, and severe). Furthermore, these AE categories will be presented graphically over time as percentage of subjects with a respective AE at a respective visit according to the definition as given in Section 3.1.1. These summaries will also be presented for the additional supportive treatment groups placebo feeder + anifrolumab 300 mg LTE, and anifrolumab 150 mg feeder + anifrolumab 300 mg LTE.

Infections, opportunistic infections, and non-opportunistic infections will be summarised with the same subcategories as given above. This summary will also be presented for the additional

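### The SAP's definition of an AE at a visit includes the next infusion date, so an infusion-day reaction after the first infusion counts at two visits in the by-visit reaction plots

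*SAP*

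**What the plan says.** SAP 3.1.1 has a separate rule for the by-timepoint analysis of anaphylaxis, hypersensitivity and infusion-related reactions. An event belongs to a visit if its onset is on or after (≥) the infusion day of that visit and on or before (≤) the "date of administration of investigational product at the following visit". For the last infusion the upper limit is 84 days after the last dose. Events with missing or partial dates go to the earliest possible visit in the study that recorded them. Nothing is said about complete dates that fall on a boundary.

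SAP 4.2.1.1 uses this definition for plots in which these reactions are "presented graphically over time as percentage of subjects with a respective AE at a respective visit".

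The SAP treats other date boundaries with more care:

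- In SAP 3.1.1, treatment and follow-up are split with ≤ and >, and Year 2 ends strictly before the "date of first administration of investigational product in LTE study plus 364 days". Years 3 and 4 follow the same pattern.
- For placebo subjects who switch to anifrolumab, SAP 3.1.1 deals with the first LTE dosing day by study of recording. In the Randomised Placebo group, events from that day on "will not be considered in the categories above, except for those with an onset on the day of first dose" in the LTE and recorded in the feeder study.
- Year 1 and Year 2 (SAP 3.1.1), and the Week 52 and Gap windows (Table 2 in SAP 4.1.2), do share LTE Day 1, but a separate sentence settles where that day goes.

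**The concern.** The shared day is the one on which these events are most likely to start. Protocol 6.5.2 offers its definition as a way to "make the diagnosis of anaphylaxis during infusion with investigational product", and Protocol 7.2.4 requires monitoring during every infusion and for 1 to 2 hours afterwards. A program that follows the SAP would show an infusion-day reaction at its own infusion and also at the previous one, about four weeks before it happened.

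The plots exist to show where in the dosing course reactions occur. Under the written rule, every visit except a subject's last also takes in the next infusion day's reactions. A rise at one infusion then appears one infusion early, and a visit at which nobody reacted can show a reaction.

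**Working it through.** **Inputs**

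- Window limits: SAP 3.1.1. Write d(k) for the date of infusion k and K for the subject's last infusion. An onset on date t belongs to visit k if d(k) ≤ t ≤ d(k+1), and to visit K if d(K) ≤ t ≤ d(K) + 84.
- LTE infusions: 39, every 4 weeks (SAP 1.2).
- Feeder infusions: 13. This is inferred from the last administration at Visit 13, Week 48 (SAP 4.2.3.1), with one infusion per visit. The full course is then 13 + 39 = 52.
- Reaction frequency, and the share of onsets on an infusion day: not given in the documents. All values below are assumptions.

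The plan gives no figure of its own to reproduce.

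**Step 1: the overlap**

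Take infusions on LTE Days 1, 29 and 57. The window for the first runs from Day 1 to Day 29, and for the second from Day 29 to Day 57. A reaction on Day 29 is in both. In general t = d(k+1) satisfies the rule for k and for k+1; only t = d(1) satisfies one rule. Any date strictly between two infusions falls in exactly one window.

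- LTE only: 39 − 1 = 38 of 39 infusion days are counted twice.
- Feeder plus LTE: 52 − 1 = 51 of 52.
- One reaction on each of 39 infusion days gives 1 + 2 × 38 = 77 visit counts for 39 reactions (77/39 = 1.97).
- With a strict upper limit the windows become Days 1 to 28, 29 to 56 and so on. The same 39 reactions give 39 counts, and no infusion day is counted twice in either series.

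The feeder-recorded rule already settles one of these days, the first LTE dosing day, for events recorded in the feeder study.

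**Step 2: size at a plotted point**

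Let p(k) be the true percentage at infusion k and s the share of onsets on the infusion day, with no subject reacting at consecutive infusions. Then

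shown(k) = p(k) + s × p(k+1) for k < K, and shown(K) = p(K).

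*Constant rate.* The ratio shown/true is 1 + s: 2.0 at s = 1, 1.5 at s = 0.5 and 1.25 at s = 0.25. If reactions at successive infusions are instead independent, with s = 1, the shown value is 1 − (1 − p)²: 1% becomes 1.99% and 2% becomes 3.96%. If 25% of later reactions are in subjects who also reacted at the previous infusion, the ratio at s = 1 is 1 + 0.75 = 1.75.

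*Front-loaded: 2%, 1%, then 0.2% at each later infusion of the series.*

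| Infusion | True | s = 0.25 | s = 0.5 | s = 1 |
|---|---|---|---|---|
| 1 | 2% | 2.25% | 2.5% | 3.0% |
| 2 | 1% | 1.05% | 1.1% | 1.2% |
| 3 | 0.2% | 0.25% | 0.3% | 0.4% |

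*80% of reactions at the first infusion, the rest spread evenly.* The sum over all points is inflated by 1 + 0.2 × s, which is 1.10 at s = 0.5 and 1.20 at s = 1. With 52 infusions and s = 1, the first point goes from 80 to 80 + 20/51 = 80.4 per 100 reactions, hardly a change. The small later points, except the last, still double.

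**Step 3: reach**

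Only the by-timepoint analysis uses this window. Event rates and overall counts use the treatment and follow-up categories. The time-to-event analyses use first onset. None of these contains the overlap.

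**The case against.** The strongest case is that this is a one-sign slip in a descriptive plot. The same section of the SAP requires an overall table of these reactions by subject, and Protocol 8.5.1 has all AEs listed, so the plots can be checked. No decision rests on them. All of that stands and limits the weight of the point. It does not make the plotted percentages right.

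A strict upper limit alone would credit an onset on an infusion day, but before the infusion, to a dose not yet given. That is true, but the current rule already counts such an event at that visit as well as the previous one. Clock times can separate the two cases where they exist.

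Three stronger readings are tempting and not supported:

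- A reader might infer that this is the only place where SAP windows share a day. It is not: LTE Day 1 is shared in Table 2 and at the Year 1/Year 2 boundary. The difference is that those cases carry a sentence that settles the day.
- A reader might size one placebo reaction as 1 in about 115 LTE placebo subjects (575/5), or 0.87%. SAP 4.2.1 puts safety summaries on combined feeder-plus-LTE groups unless stated otherwise, and SAP 4.2.1.1 adds only two further combined groups for these plots. Those denominators include subjects who never entered the LTE, so one reaction is a smaller percentage than that.
- A reader might take a doubling as the expected result. Protocol 1.3 mentions delayed as well as acute hypersensitivity, so s could be well below 1 for that category. In most combined groups the series also starts at the first feeder infusion, so an early peak need not fall in the LTE.

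**Conclusion.** The definition is wrong as written. Followed literally, it counts a fully dated reaction on any infusion day after the first at two visits, apart from the feeder-recorded exception on the first LTE dosing day. This follows from the two inclusive limits and depends on no assumed rate.

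The size does depend on assumptions. About a doubling of every point except the last needs all onsets on infusion days, a constant rate and no subject reacting at consecutive infusions. The inflation is smaller when fewer onsets fall on infusion days, and smaller in total when most reactions occur at the first infusion. The effect is confined to the descriptive by-visit plots; the primary AESI and SAE rates are untouched. It should still be corrected, because it distorts the timing that the plots are meant to show.

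**What to change.** In SAP 3.1.1:

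1. Change the upper limit to onset before (<) the date of administration at the following visit with an infusion. The added words also cover a following visit at which no dose was given, where the present limit is undefined.
2. Keep the limit of 84 days after the last dose for the last infusion.
3. Keep feeder-recorded events on the first LTE dosing day with the feeder visit, in line with the rules elsewhere in that section.
4. Where onset time and infusion start time are both recorded, assign an infusion-day onset before the infusion start to the previous infusion. Protocol 6.6.3 lists "The date and time when the AE started and stopped" among the AE variables, and the infusion definition in SAP 3.3.4 requires that "Start time and end time of study drug infusion are not missing".

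The cost is one sign and two short clauses in the SAP, with the matching change in the plot program. No new data are needed.

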#### **3.1.1.1 Other significant adverse events**

During the evaluation of the AE data, a PRA medically qualified expert will review the list of AEs that were not reported as SAEs and discontinuations due to AEs.

Based on the expert's judgment, significant AEs of particular clinical importance may, after consultation with the Astra Zeneca Global Patient Safety Physician, be considered other significant AEs and reported as such in the CSR.

Examples of these are marked haematological and other laboratory abnormalities, and certain events that lead to intervention (other than those already classified as serious), dose reduction, or significant additional treatment.

#### **3.1.2 Vital signs**

The following variables will be explored:

- Pulse (beats per minute)
- Systolic blood pressure (mmHg)
- Diastolic blood pressure (mmHg)
- Respiration rate (breaths per minute)
- Body temperature (°C)

Changes from baseline will be calculated for post-baseline assessments with a corresponding baseline observation.

Where applicable, absolute values will be compared to the reference ranges [REDACTED] and classified as low (below range), normal (within range or on limits), or high (above range). All values (absolute and change) falling outside the reference ranges will be flagged.

Post-baseline values will be classified as treatment-emergent laboratory/vital signs changes (TELVC) according to reference ranges [REDACTED]

For infusion visits, only measurements before the start of investigational product infusion will be considered for by-visit presentations. In the case of multiple measurements before the start of investigational product, the first measurement will be used for by-visit presentations, but all measurements will be considered for the TELVC classification.

